This is an experimental single-blinded randomized clinical trial conducted in the operating room for elective surgery at the dr. Cipto Mangunkusumo Hospital, a tertiary national referral hospital in Jakarta, Indonesia from June to August 2020. The sample size of 62 patients was calculated using numerical hypothesis testing formula for two unpaired populations with an

additional 10% of presumed sample dropout. Ethical clearance was obtained from Universitas Indonesia Ethical Board Committee.

All adult patients (18-65 years old), ASA I-II, with Body Mass Index (BMI) of 18 – 30 kg/m² scheduled for elective surgical procedures under general anaesthesia were included. All subjects provided written consent. We exclude patients with a difficult airway, pregnancy, cardiac condition, and neuromuscular disease.

The self-assembled modified Macintosh video laryngoscope (SAM-VL) used in this study was constructed from a portable video camera with a Wi-fi connection (Wi-fi Endoscope Video Camera model YPC99) attached to a no. 4 Macintosh Laryngoscope blade (Riester no.7040). The video signal is transmitted to an Android-based mobile phone (Android version 7.0). The portable 2 megapixels video camera is 8 mm in diameter with 8 LED lights for adjustable lighting level and 3 meters cable length. Video resolution output is 640x480 pixels (VGA) and 1280x720 pixels (HD). The camera has a 70° visual angle with a focal length of 4– 6cm and is water-resistant. The camera was taped to the Macintosh blade at a distance of 5 cm from the distal end of the blade, using transparent waterproof Leukofix[®] tape. After installation, the camera was oriented on a flat plane to set the desired image. The video images are then viewed on the mobile phone screen using the Y-camera app (downloadable for free in Google Play Store for Android). The total cost for this camera device assembly was Rp260.000 (roughly 20 USD), excluding the Android phone. After intubation, the camera is removed from the Macintosh blade and the camera tip that enters the patient's oral cavity is flushed with running water and washed with soap for at least two minutes, using a soft bristle brush to remove any soil if needed. After drying, the camera is wiped with a 70% alcohol swab before the next procedure.

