Randomization was done with tables and then presented in a closed envelope when the patient arrived at the operating room to determine the intervention group: (1) the Self-Assembled Modified Macintosh Video laryngoscope (SAM-VL) group or (2) the McGrath MAC[®] video laryngoscope (McGrath) group. The laryngoscopist is the one who opened the envelope. A research assistant helped to prepare the laryngoscope according to the randomization results.

Anaesthesia monitoring was conducted following ASA standard and included ECG, non-invasive blood pressure, pulse oximeter, etCO₂, and temperature. Initial hemodynamic status

of the patient before induction including systolic, diastolic, mean arterial pressure, pulse, and peripheral oxygen saturation was noted.

Anaesthesia was co-induced intravenously with fentanyl 2 µg/kg, propofol 2 mg/kg, and rocuronium 0.6 mg/kg. Medications were titrated to effect. Subjects were given positive pressure mask ventilation with 80% oxygen for 3 minutes. Hemodynamic status was recorded three times: (1) pre-induction, (2) at 3 minutes after co-induction medications were given, and (3) after tracheal intubation in confirmed.

The intubation time “A” recording began when the tip of the laryngoscope blade passed through the incisors until the operator was able to achieve the best visualization of the glottis. The “B” intubation time recording began when the operator received visualization of the glottis and ended after the ET tube was confirmed to enter the trachea. Intubation time “B” consists of two components, insertion of the ETT into the vocal cords and connecting the breathing circuit so that the etCO₂ wave appeared on the monitor. When inserting the ET tubes, all operators were assisted with a stylet. To minimize the delay in connecting the circuit, one assistant was present to help the operator.

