Intubation was done using ET tube No.7.5 for men and No.7 for women with the help of a stylet. Subjects underwent laryngoscopy and intubation with either McGrath MAC[®] video laryngoscope or SAM-VL according to randomization. During visualization of the glottis, the operator mentioned the POGO (Percentage of Glottic Opening) score visualized, with a scale ranging from 0–100%. Successful intubation was confirmed by capnography tracing. The SAM-VL can record both photo and video formats. McGrath MAC[®] screen can only be used for visualization, but the image cannot be recorded. Thus, a smartphone video camera is used to record images from the McGrath MAC[®] screen.

One attempt to intubate was noted if the ET tube was successfully placed into the trachea on the first attempt. If the laryngoscope blade was removed from the mouth and then reinserted, consequently the researcher noted the number of intubation attempts. If the intubation attempt was unsuccessful 3 times and/or the intubation time exceeds 120 seconds, the subject was dropped out.

If during the procedure an emergency or desaturation of $\leq 90\%$ occurred, it would be managed following ALS algorithms and the subject was dropped out from the study. Any complication throughout the procedure was noted. This study also includes a survey to evaluate the operator's subjective experience using three questionnaires in Likert scale format. The items evaluated are ease in blade insertion, device maneuverability, glottis visualization, and overall satisfaction rating.

The results were calculated using the *Statistical Package for Social Scientists* (SPSS) 24. Analysis of the duration of intubation (numerical data) was done with an unpaired *t-test* for data with normal distribution, and Mann-Whitney if the distribution was not normal. The results were considered significant if the p-value was < 0.05 .

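### Patients dropped for failed or slow intubation have no place in the time comparison, and the plan does not say which intubation time is tested

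*Combined protocol and SAP*

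**What the plan says.** All the relevant text is in Research Methods of the combined protocol and SAP.

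- **Dropping.** The paragraph on attempts says that if intubation was "unsuccessful 3 times and/or the intubation time exceeds 120 seconds, the subject was dropped out". The next paragraph says that an emergency or a desaturation to 90% or below would be "managed following ALS algorithms and the subject was dropped out from the study".
- **Times.** Time A runs from the blade passing the incisors "until the operator was able to achieve the best visualization of the glottis". For time B, "recording began when the operator received visualization of the glottis and ended after the ET tube was confirmed to enter the trachea". Both are called intubation time, and no total is defined.
- **Analysis.** The sentence that names the outcome begins "Analysis of the duration of intubation (numerical data) was done with an unpaired" and identifies no interval. It then lets the sample decide between two tests, the t-test being used "for data with normal distribution, and Mann-Whitney if the distribution was not normal". No criterion for normality, effect measure or confidence interval is given.
- **Sample size.** The 62 patients come from a "numerical hypothesis testing formula for two unpaired populations" with an "additional 10% of presumed sample dropout". Power, difference, standard deviation and allocation ratio are not given.

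**The concern.** Three failed attempts, a long intubation and desaturation are outcomes that the laryngoscope can influence. If such patients leave the time comparison, what remains is a comparison of successes, and the two groups of successes need no longer be alike. A device that is quick in easy patients and fails in the others would then show only its quick times.

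The unnamed interval is a second, separate gap. Time A mostly reflects obtaining the view, and time B passing and confirming the tube. The Background itself says that tube passage can be harder even when the cords are clearly seen, so the choice of interval could decide the answer. The 120 s limit has the same gap, because it does not say which time it refers to.

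The rule for choosing the test is a minor matter. It leaves the quantity compared (means or ranks) to be settled by how the sample looks.

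**Working it through.** **1. The plan's own figure.** The 62 cannot be derived in full, because power, difference and standard deviation are missing. The dropout step can be matched: 56 × 1.1 = 61.6, rounded up to 62 (or 55 / 0.9 = 61.1, also 62). On the first reading 28 per arm are analysed and 62 − 56 = 6 are presumed lost. A sample size inflated for dropout fits with dropped patients being left out of the analysis.

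**2. How uneven the dropouts could be.** Assume 31 per arm. If all 6 fall in one arm, that is 6/31 = 19.4% v 0%. The two-sided Fisher p is 2 × C(31,6) / C(62,6) = 2 × 736,281 / 61,474,519 = 0.024. A split of 5 v 1 gives p = 0.195, and 4 v 2 gives 0.671.

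**3. What leaving failures out hides, in seconds.** Assume 31 per arm and a mean of 38 s among successes in both arms. Counting k failures in one arm at 120 s adds k × (120 − 38) / 31 to that arm's mean: 2.6 s for k = 1, 7.9 s for k = 3 and 15.9 s for k = 6. Leaving them out shows 0 s.

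**4. Chance of p < 0.05 with failures dropped or ranked worst.** Simulation with 31 per arm and log-normal times, log-SD 0.4. Where one device is faster, or times are shifted, the difference is 0.762 log-SD, the value giving 80% power on the log scale at 28 per arm. That is 0.762 × 0.4 = 0.305 on the log scale, or a median about 26% shorter (exp(−0.305) = 0.737). Failures are independent of the underlying time. The comparison without failures uses Welch; worst rank uses Mann-Whitney with failures tied last.

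| Scenario | Failures dropped | Worst rank |
|---|---|---|
| Faster device fails 20% v 2% | 0.76 | 0.16 |
| Faster device fails 10% v 2% | 0.79 | 0.48 |
| Equal times, failures 2% v 20% | 0.05 | 0.23 |
| Equal times, failures 2% v 10% | 0.05 | 0.08 |
| Times shifted, failures 5% in both | 0.78 | 0.72 |
| Times shifted, failures 10% in both | 0.77 | 0.62 |

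**5. Which time is tested.** Welch test, 28 per arm, log-SD 0.4, assumed A/B medians of 10/25, 15/15 and 8/40 s, with several A–B correlations. A difference confined to A is detected in 0.76–0.77 of trials on A, 0.04–0.05 on B and 0.09–0.54 on A + B. With no true difference, testing all three at 0.05 gives at least one significant result in 0.09–0.11.

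**6. The choice of test.** 28 per arm, Shapiro-Wilk in each arm (assumed, as no criterion is stated), log-SD 0.3 and 0.5. The type I error of the two-stage rule is 0.055 and 0.049; its power is 0.79 and 0.78, against 0.79 and 0.75 for Welch. The target matters only when the arms differ in spread. With equal means and log-SD 0.3 v 0.6, the two-stage rule rejects in 0.18 and Welch in 0.06. With equal medians and the same spreads the order reverses, 0.07 v 0.11.

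**The case against.** - **Exclusion is not stated.** The text says that these patients were dropped out, and never that they were excluded from analysis. The Background lists first-attempt success and complications as separate comparisons, and attempts and complications are recorded, so time is not the only place where failure could appear. This stands: exclusion is an inference, though a strong one. No analysis set, cap or ranking rule returns these patients, one never intubated has no end to time B, and the document does not say that dropped patients are kept for the other outcomes.
- **The failure rates are extreme.** Enrolment is limited to ASA I–II, BMI 18–30 and no difficult airway. Nothing in the document suggests 20% failure, and the 10% allowance covers dropout for any reason. This also stands. At 2% v 10% with equal times, worst rank rejects in only about 0.08, so the failure counts per arm carry most of the information.
- **A reader might infer that choosing the test from the data inflates type I error.** The calculations do not support that; the rate stays near 0.05. The 0.18 v 0.06 contrast needs one log-SD to be double the other, and each test rejects when its own target differs. Preferring mean seconds is partly a matter of taste.
- **A reader might infer that A + B counts some time twice**, because A ends at the best view and B begins when a view is received. One shared boundary, loosely worded, is the more natural reading, and the document does not describe two clock events.
- **Timing.** Conduct is given as June to August 2020, the document is dated December 2020, and the analysis is in the past tense. Advice to specify in advance therefore has limited force. The dates alone do not show that any choice was made after seeing results.

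**Conclusion.** The concern holds as a minor one, in this order of weight.

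1. The dropping rule depends on outcomes the device can influence, and nothing brings the dropped patients back into the time comparison. The 0.76 v 0.16 contrast shows what this can do at the far end; at milder imbalances the effect is smaller. The document gives no evidence that failures in fact differed between the devices.
2. The tested interval, and the time to which the 120 s limit refers, are not identified. A difference in A alone can be seen on A and missed on B or the total.
3. Choosing the test by the look of the data leaves means or ranks open, without material effect on type I error or power.

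The simulated figures rest on log-normal times and on assumed spread, medians, correlation, failure rates and 31 randomised (28 analysed) per arm. None of these is in the document. Points 2 and 3 follow from the text alone; point 1 rests also on the inference that dropped means not analysed.

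**What to change.** - **Name one tested interval**, for example from the blade passing the incisors to the etCO₂ wave, with A and B as secondary. State which time the 120 s limit refers to.
- **Report dropped patients by arm and reason.**
- **Analyse all randomised patients with a worst-rank Mann-Whitney.** Tie failed intubations and times over 120 s at the worst rank. Rank patients dropped for desaturation or an emergency worst as well, with their own time, if intubated, in a sensitivity version. Give the probability that one device does better, U/(n₁n₂), with a 95% CI.
- **Beside it, use one fixed analysis of recorded times** with an effect estimate and 95% CI, for example the Welch difference in mean seconds. Include every patient with a recorded time, also those over 120 s or with desaturation, and state that patients never intubated are not in it.
- **Label the analysis post hoc** if it is adopted after the data were seen.

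The cost is a few lines of text and one added analysis, with no extra patients. The arm and reason of each dropped patient must have been kept, which the document does not say. Worst rank loses power when both devices fail equally often (0.72 v 0.78 at 5%, 0.62 v 0.77 at 10%). The ranking of desaturations can matter: if dropouts are 6 v 0, all desaturations, and times are equal, the two versions differ on significance in 0.22 of trials, so both should be shown. With log-normal times Welch has up to 0.03 less power than the two-stage rule. A total time can dilute a difference confined to A, which is why A and B stay as secondary.

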Date: December 14th 2020

**Self-Assembled Modified Macintosh Video laryngoscope versus McGrath
MAC[®] Video laryngoscope: Which is Better?**

[name], [name], [name]
Department of Anesthesiology and Intensive Care
Faculty of Medicine, Universitas Indonesia–RSUPN dr. Cipto Mangunkusumo
[name]

Background

Endotracheal intubation, the gold standard in definitive airway management, is a procedure for inserting an endotracheal tube (ET tube) with the help of a laryngoscope. A study showed that 94% of intubation done by skilled operators would be successful in 1 to 2 attempts. In contrast, non-skilled operators had only 82% first-attempt success rate with 13.2% requiring 3 or more attempts, and 10.3% taking over 10 minutes.^{1,2} One of the biggest upgrades in the recent decade to improve this success rate is the addition of video camera to a laryngoscope, reintroducing the device as a Video laryngoscope (VL). McGrath MAC[®] laryngoscope is one of the most widely used commercial video laryngoscopes that utilize a modified Macintosh blade, with a video camera and a light source attached at the end of the blade. The image is displayed in the *liquid-crystal display* (LCD) monitor mounted on the handle of the blade.^{3,4}

VL has been shown to improve visualization of the larynx.^{5,6,7,8} However, several studies showed that intubation time with McGrath MAC[®] is the same or even longer compared to conventional macintosh blades.⁷⁻¹⁰ Insertion of ET tube through the vocal cords is also more difficult even though it is clearly visualized because the ET tube is in contact with the anterior tracheal wall, and therefore a stylet is needed to bend the tip of the ETT to an angle $> 35^\circ$.^{3,10,11} McGrath's blades are also less effective than the wider sized Macintosh blades to displace the tongue and expanding the area for visualization of the larynx and ET tube insertion¹⁰

Despite the advantages of video laryngoscope, the expensive price becomes a problem, especially in developing countries.^{6,12} As an alternative, we modified a classic Macintosh laryngoscope by attaching a flexible fiber optic-like camera to its blade. We compared the intubation time, success first attempt rate, laryngeal visualization, complications, and user satisfaction between this self-assembled video laryngoscope and McGrath MAC[®].

Research Methods

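### Does the plan need to prespecify a between-device difference and 95% confidence interval alongside its p-value for intubation time?

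*Combined protocol and SAP*

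**What the plan says.** The statistical text is the final paragraph of Research Methods. It names SPSS 24 and continues "Analysis of the duration of intubation (numerical data) was done with an unpaired" t-test when the data are normal, with Mann-Whitney otherwise. The decision rule is "The results were considered significant if the p-value was < 0.05". No effect measure, interval, margin or minimum important difference appears there or elsewhere. The paragraph is equally silent on group means, medians and counts.

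The Background sets out the comparison: "We compared the intubation time, success first attempt rate, laryngeal visualization, complications, and user satisfaction". The title puts the question as "Which is Better". Research Methods gives 62 patients in total, from a "numerical hypothesis testing formula for two unpaired populations" plus a 10% dropout allowance, without stating an SD, target difference, power or sidedness.

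**The concern.** A question about which device is better is also a question about by how much, especially when a camera assembly costing roughly 20 USD is set against an expensive commercial device. A p-value compared with 0.05 does not give seconds gained or lost. With about 30 patients per arm, two results just either side of the threshold can be compatible with nearly the same range of true differences and still receive opposite labels. A non-significant result could also be misread as showing that the devices perform alike. If the report held only p-values, a reader could not tell a precise null from an uninformative one.

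**Working it through.** **Inputs.** From Research Methods: 62 patients, 10% allowance, threshold 0.05. Assumed, because not stated: 1:1 allocation and a two-sided test. With no SD given, differences in time are in SD units.

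**The plan's own figure.** 62 cannot be derived from stated inputs. It does fit 28 per arm plus 10%: 28 × 1.10 = 30.8, rounded up to 31, and 2 × 31 = 62. So 28 and 31 per arm bracket the likely analysed number.

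**Interval width for time.** Half-width = t(0.975, 2n − 2) × SD × √(2/n).

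- 28 per arm: t(0.975, 54) × √(2/28) = 0.536 SD.
- 31 per arm: t(0.975, 60) × √(2/31) = 0.508 SD.

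At 28 per arm, assumed SDs of 5, 10 and 20 s give about ±2.7, ±5.4 and ±10.7 s.

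**Results near the threshold, 28 per arm.** The observed difference for a given p is t(1 − p/2, 54) × √(2/28), and the interval adds and subtracts 0.536.

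| p | Difference (SD) | 95% CI (SD) |
|---|---|---|
| 0.04 | 0.56 | 0.03 to 1.10 |
| 0.06 | 0.51 | −0.02 to 1.05 |

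The two ranges nearly coincide. The same happens in any trial judged at 0.05, so this does not mark a fault particular to this plan.

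**Does the planned analysis already contain the missing quantity?**

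- *t-test branch.* The statistic is the mean difference divided by its standard error. The interval is that difference ± t(0.975, 2n − 2) × the same standard error. It excludes zero exactly when p < 0.05. Nothing has to be collected or chosen.
- *Mann-Whitney branch.* The test gives no difference in seconds. The usual companion is the Hodges-Lehmann estimate, the median of all pairwise differences (28 × 28 = 784, or 31 × 31 = 961), with an interval from the same rank distribution. It uses the same data but has to be requested.

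**What reporting an interval would not alter.** With the t-test, the chance of missing a true 0.5 SD difference is 55% at 28 per arm and 51% at 31 (power 0.451 and 0.491). These figures describe the sample size and are identical with or without a reported interval. N and alpha are also unchanged.

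**First-attempt success.** With equal rates in both arms, the Newcombe half-width at 28/31 per arm is 20/19 points at 82% and 16/15 points at 94%. Both rates are weak inputs: "non-skilled operators had only 82% first-attempt success rate" concerns a group that may not match this trial's operators, and "94% of intubation done by skilled operators would be successful in 1 to 2 attempts" is not a first-attempt rate. The plan names no test for this outcome at all, so its gap is not that a p-value stands alone.

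**The case for a change.** The best case for a change is that prespecifying the estimate costs one sentence and fixes what will be reported before anyone chooses. This has most force on the Mann-Whitney branch, where several summaries are possible and the test supplies none in seconds. It is also true that a half-width of about half an SD leaves much unresolved, and a reader should see that.

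What stands is that no estimate or interval is specified, and that a good report should give one. What does not stand is the step from silence to a commitment. A paragraph that lists software, tests and a threshold does not promise to omit means, medians or differences. The Background remark that McGrath time "is the same or even longer compared to conventional macintosh blades" compares McGrath with another blade and says nothing about SAM-VL against McGrath. A safeguard against calling a non-significant result equivalence would answer a claim the plan never makes.

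An interval would not repair two nearby matters either. Research Methods defines times A and B without saying which is tested, and subjects with three failed attempts, times over 120 s or desaturation are dropped. An interval computed on those who remain need not cover the randomised comparison.

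**Conclusion.** No change to the plan follows. The difference tests fit the title's question, the threshold is conventional, and following the text exactly gives a valid test result. No stated number or rule is shown to be wrong. The gap is one of reporting detail that an analyst ordinarily fills: the mean difference and t-based 95% interval with the t-test, or the Hodges-Lehmann shift and its interval with Mann-Whitney. The expected half-width is about 0.54 SD at 28 per arm and 0.51 SD at 31, assuming 1:1 allocation and a two-sided 95% level. It cannot be given in seconds without an assumed SD.
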